# 8.3.1.1 Primary efficacy variable

 Progression-free survival (PFS), defined as the time (in days) from randomization to PD or death from any cause (if no progression is documented). The actual date of tumor assessments will be used for this calculation. PFS for patients without PD or death at the time of analysis will be censored at the date of their last tumor evaluation. PFS for patients who have neither tumor assessments nor death after baseline will be censored at Day 1.

# 8.3.1.2 Secondary efficacy variables

- Objective tumor response rate (ORR) assessed in all patients up to the time of analysis of PFS. ORR is defined as the proportion of patients who have a best response rating over the whole duration of the study (i.e. until time of analysis of PFS) of complete response (CR) or partial response (PR) according to the Lugano Classification and for patients with WM a response rating of CR, very good partial response (VGPR), PR, or minor response (MR) according to the Owen Criteria. Detailed instructions on tumor assessment are provided in Appendix 14.4.
- Duration of response (DOR), defined as the time (in days) from first observed tumor response (CR, VGPR, PR, or MR) until PD or death from any cause, whichever is earlier. DOR will only be defined for patients with at least one CR, VGPR, PR, or MR. Patients without PD or death at the time of analysis will be censored at the date of their last tumor evaluation.
- Complete response rate (CRR), assessed in all patients up to the time of analysis of PFS.
- Time to progression (TTP), defined as the time from randomization to PD or death related to PD, whichever is earlier. The actual dates of tumor assessments will be used for this calculation. TTP for patients without PD at the time of analysis or death not related to progression will be censored at the date of their last tumor evaluation. TTP for patients who have neither tumor assessments nor death related to PD after baseline will be censored at Day 1. Death related to PD is considered to be any death except for:
  - Death due to an AE unrelated to progression
  - o Death with a specification of "other" as reason (which excludes PD)
- Overall survival (OS), defined as the time (in days) from randomization until death from any cause. OS of patients alive at the time of analysis will be censored at the last date they were known to be alive.

09 FEB 2023 Page: 92 of 151

• Time to deterioration in DRS-P of at least 3 points, as measured by the FLymSI-18 questionnaire. Patients will be considered as "censored" at the date of their last tumor evaluation, if the reason for stopping treatment is not related to PD. Patients dropping out due to progression-related reason or experiencing a PD event or death due to any reason will be considered as having had their decline in DRS-P at the date of their last tumor evaluation.

• Time to improvement in DRS-P of at least 3 points, as measured by the FLymSI-18 questionnaire, will be evaluated for patients with a baseline DRS-P score of 30 points or less (i.e. patients who still have room for improvement in symptoms). Patients will be considered as "censored" at the date of their last tumor evaluation, if the reason for stopping treatment is not related to PD. Patients dropping out due to progression-related reason or experiencing a PD event or deaths due to any reason will be considered censored at the largest observation time (of events and censoring in all patients evaluated for improvement), plus 1 day.

Further sensitivity analyses for the DRS-P analyses will be described in the SAP (e.g. might involve different handling of the last response status for that patient or considering PD and death as censored). Considering at least 3 points decline or increase, respectively, to be an important change with regard to DRS-P is the current assessment. The important change for DRS-P is however under continuing research by the developer of the questionnaire. Therefore, the value of 3 points might be updated in the SAP, considering forthcoming research findings.

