## 2. Study objectives

The primary objective of this study is:

• To evaluate whether copanlisib in combination with rituximab is superior to placebo in combination with rituximab in prolonging progression-free survival (PFS) in patients with relapsed iNHL who have received one or more lines of treatment, including rituximab, and who either had a treatment-free interval of ≥ 12 months after completion of the last rituximab-containing treatment, or who are unwilling to receive chemotherapy/for whom chemotherapy is contraindicated on reason of age, comorbidities, and/or residual toxicity

The secondary objectives of this study are to evaluate:

- The following characteristics of disease-related symptoms: "time to deterioration" and "time to improvement"
- Other radiological and clinical indicators of treatment efficacy
- Safety and tolerability of copanlisib

The other objectives of this study are to evaluate:

- Pharmacokinetics
- Biomarkers
- Quality of life

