# 8.3.1.3 Other efficacy variables

- AUC across all data of FLymSI-18 DRS-P subscale score
- FLymSI-18 total and subscale scores (DRS-P, DRS-E, TSE, FWB), and time to onset of physical symptoms of lymphoma based on the DRS-P subscale
- Performance status (ECOG)

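### Time to DRS-P deterioration is tested as a symptom endpoint but counts progression-related dropout, PD and any death as decline, so a PFS effect alone can make it significant

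*Protocol*

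**What the plan says.** Protocol Section 2 lists as a secondary objective "The following characteristics of disease-related symptoms", namely time to deterioration and time to improvement. Section 8.4.2.3 puts time to deterioration in both confirmatory sequences at one-sided 0.025. In Europe it comes third, in the FAS, after PFS and ORR. In the United States it comes fourth, in the combined FL and MZL population, after PFS in the FAS and then PFS and ORR in that population. Section 8.4.2.2 has it analysed in the same way as PFS.

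Section 8.3.1.2 gives the definition: a drop of 3 or more points on the FLymSI-18 physical-symptom subscale. Patients leaving for a progression-related reason or "experiencing a PD event or death due to any reason will be considered as having had their decline in DRS-P", dated at the last tumor evaluation. Other patients are censored "at the date of their last tumor evaluation, if the reason for stopping treatment is not related to PD". PFS (Section 8.3.1.1) is "defined as the time (in days) from randomization to PD or death from any cause", so every PFS event is also a deterioration event unless a questionnaire decline came first.

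Section 8.3.1.2 also says that further DRS-P sensitivity analyses will be in the SAP, and gives "considering PD and death as censored" as one possible example. Section 8.3.1.3 lists "AUC across all data of FLymSI-18 DRS-P subscale score" and "time to onset of physical symptoms of lymphoma based on the DRS-P subscale" as other efficacy variables.

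SAP Supplement 1.0 (Section 6.2) plans both DRS-P analyses one year after primary completion. Supplements 2.0 and 3 repeat them, and Supplement 3 drops only the DRS-P subgroup analyses. Main SAP version 6.0 is not among the documents.

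**The concern.** The name promises a symptom result; the definition delivers symptom decline, progression or death. The fixed sequence gives no protection, because the PFS effect that opens the gate is itself part of the later endpoint. A rejection could then be read as a patient-reported benefit when symptoms were no different between the arms.

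A second and conditional issue is the censoring date. After a stop for reasons other than PD, scans continue in Active follow-up until PD or new therapy (Section 7.1.2.5.2). If the last tumor evaluation can be a scan taken after questionnaires have ended, time without symptom measurement counts as time without decline. If such stops are more common on copanlisib, that favours copanlisib.

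**Working it through.** **The plan's own figure.** Inputs from Section 8.6 and Table 8–1: 190 events, HR 0.61, 2:1 allocation, one-sided 0.025. Schoenfeld: power = Φ(√(d × 2/3 × 1/3) × |ln HR| − 1.96) = Φ(√42.22 × 0.494 − 1.96) = Φ(1.25) = 89.5%, as stated. The other Table 8–1 rows also reproduce (78.7%, 98.5%, 94.3%). The documents state no power for the DRS-P test.

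**Composite hazard ratio with no symptom effect.** The control PFS median is 14 months (Section 8.6). Let m be the symptom-decline median, the same in both arms (an assumption). With exponential times, ln 2 cancels:

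HR = (1/m + 0.61/14) / (1/m + 1/14)

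For m = 24: (0.0417 + 0.0436) / (0.0417 + 0.0714) = 0.0852 / 0.1131 = 0.75.

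**Rejection rate.** Two simulations used N = 458 for the FAS, 2:1, a cut at the 190th PFS event, about 30% dropout and an unstratified log-rank test. A (3,500 trials per scenario) uses exact event times. B (4,000 trials) uses the protocol scan schedule, assumed 4-weekly questionnaires, and assumes that 10% of PFS events are deaths. The FL+MZL column is from A, simulated as its own trial with N = 370 and 140 events.

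| m (months) | Composite HR | A: FAS | A: FL+MZL | B: FAS | B: FAS, given PFS significant |
|---|---|---|---|---|---|
| 6 | 0.88 | 21% | 16% | 18% | 19% |
| 12 | 0.82 | 38% | 30% | 34% | 37% |
| 24 | 0.75 | 59% | 48% | 55% | 59% |
| 36 | 0.72 | – | – | 66% | 71% |
| 48 | 0.70 | 76% | 63% | – | – |
| 60 | 0.68 | – | – | 76% | 82% |

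Cross-check at m = 60: B has 225 composite events, so Φ(√(225 × 2/9) × |ln 0.684| − 1.96) = Φ(7.07 × 0.380 − 1.96) = Φ(0.73) = 77%, in line with 76%.

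The share of counted declines that are PD or death is 24% to 71% in A (m = 6 to 48) and 21% to 74% in B (m = 6 to 60). If symptom and PFS times have correlation 0.6, FAS rejection in A is 9% to 78%. With PFS HR 1.00 it is 2.0% to 2.7%. With PD and death censored instead of counted, B gives HR about 1.00 and 2.6% to 3.0%.

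**Censoring date.** B was rerun with PFS HR 1 and no symptom effect, m = 12 and 24, and about 22% of copanlisib and 4% of placebo patients stopping for non-PD reasons (assumed). Questionnaires are assumed to end when treatment stops.

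| Reading of the censoring rule | HR | Rejection in favour of copanlisib |
|---|---|---|
| Last scan on or before the stop | 1.01 | 2.2–2.4% |
| Last Active follow-up scan, later PD or death still an event | 0.89–0.92 | 7.8–12.4% |
| Last Active follow-up scan, patient stays censored | 0.79–0.80 | 33–34% |

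A separate run with about 25% against 5–10% stops and a 30-day questionnaire visit gave HR 0.93–0.98 (4–10%) for the second reading and 0.83–0.91 (14–25%) for the third. With equal stops, every reading stays between 2.4% and 3.4%.

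**Supplement 3.** Amendment 12 (09 FEB 2023) ended questionnaires (Section 7.6.2); the data cut-off is 31 AUG 2023. That is 203 days, less each site's lag in adopting the amendment, in which only scans can extend event-free time.

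**The case against.** The composite is openly defined, and the objectives set the term in quotation marks, which can be read as pointing to that definition. Counting PD and death as deterioration is a recognised choice that avoids informative censoring. Section 8.3.1.2 commits to DRS-P sensitivity analyses, Section 8.4.2.4 to a between-arm AUC comparison, and Section 8.1 leaves missing-data handling to the SAP. No document claims a symptom benefit. All of this stands. It does not change what a rejection shows: the AUC is not a time-to-event analysis, the protocol gives no rule for PD or death in time to symptom onset, and the one sensitivity analysis that separates symptoms from PFS is only tentative.

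Several stronger readings are tempting but not supported:

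- *The test is invalid.* It is not: without a PFS or symptom effect, and with equal non-PD stops, it holds its level.
- *Unequal non-PD stops alone bias it.* They do not if censoring is at the last scan on or before the stop, and the text allows that reading. The bias figures also rest on an assumed questionnaire schedule. Amendment 12 ended collection, and the current protocol keeps only remnants of the schedule (Cycle 1 Day 1 and the safety visit). If questionnaires ran on through Active follow-up, the issue largely disappears. The 24.7% AE stop rate in Section 1.1.2 comes from a monotherapy study, and there is no placebo figure.
- *Dating deaths at the last scan distorts the result.* In simulation it moves the HR by 0.003 or less.
- *Time to improvement has the same flaw.* There, patients with PD or death are "considered censored at the largest observation time" plus a day, so progression never counts as a symptom gain.

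**Conclusion.** The point holds for the composite, with high confidence: the definition is explicit, and the planned PFS effect alone gives a composite HR of about 0.88 to 0.70. FAS rejection of roughly 20% to 76% shows what can happen, not a likely size. It rests on assumed symptom medians of 6 to 48–60 months and exponential times, with symptom decline independent of PFS. A rejection supports delay of symptom decline, progression or death taken together; it does not by itself show delayed symptom worsening.

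The censoring-date issue is secondary and conditional, with moderate confidence. It needs scan dates that run past the last questionnaire together with more non-PD stops on copanlisib. SAP version 6.0 may already settle it. Because the primary analysis is complete (Section 13.7.1), the consequence is now for labelling, reporting and the follow-up analyses.

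**What to change.** 1. Label the endpoint *time to DRS-P deterioration, progression or death* and limit the claim to that.
2. Report events by component: questionnaire decline, PD, progression-related dropout, death.
3. Make the questionnaire-only analysis firm and supportive, once with PD and death censored and once with them as competing events. State that censoring PD may be informative: at correlation 0.6 with no symptom effect, it gave HR 1.05 to 1.29.
4. For deterioration, censor event-free patients at the last FLymSI-18 assessment instead of the last scan, and say how PD or death after a non-PD stop is handled. The choice matters: counting later PD and death while dropping later event-free time gave HR 1.00 to 1.08 with unequal stops and no true effect. Show this beside the original result, and apply the same limit in Supplement 3.

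If SAP version 6.0 already sets these rules, align the protocol text with it. Keep the confirmatory test and the original result on record; re-dated results are post hoc.

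The cost is wording and re-derivation from data already held. The downside is less follow-up, fewer events (in simulation B at a 36-month symptom median, 90 questionnaire-only events against 245 composite events) and probably a less favourable HR.

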# 8.3.1.3 Other efficacy variables

- AUC across all data of FLymSI-18 DRS-P subscale score
- FLymSI-18 total and subscale scores (DRS-P, DRS-E, TSE, FWB), and time to onset of physical symptoms of lymphoma based on the DRS-P subscale
- Performance status (ECOG)

# 8.3.2 Safety variables

Safety variables will include treatment-emergent AEs, SAEs, laboratory parameters, and vital signs. The severity of AEs will be graded using the CTCAE v 4.03 dictionary. AEs will be classified by the investigator as related or not related to test drug. A treatment-emergent AE is defined as any event arising or worsening after start of study drug administration until 30 days after the last study drug intake (end of safety follow-up).

# 8.4 Statistical and analytical plans

### **8.4.1** Population characteristics

Demographics and baseline characteristics will be summarized by treatment group in the FAS.

A listing for the retrospective evaluation of histopathological diagnosis performed centrally at baseline will be provided. These data are exploratory.

09 FEB 2023 Page: 93 of 151

# 8.4.2 Efficacy

All efficacy analyses will be performed when at least 190 PFS events (PD by central review or death before PD) are observed in the study. Also see minimum number of PFS events that has to be observed in each of the two strata defined by the inclusion criterion (progression-free and treatment-free interval of  $\geq$  12 months after completion of the last rituximab-containing treatment vs. unwilling/unfit to receive chemotherapy). See Section 8.6.

Evaluations from central blinded review will be used for the primary efficacy analyses of primary and secondary endpoints containing radiological tumor assessments.

# 8.4.2.1 Primary efficacy analysis

All randomized patients (FAS) will be included in the primary analysis.

In order to evaluate whether copanlisib in combination with rituximab is superior to placebo in combination with rituximab in prolonging PFS in patients with relapsed iNHL who have received one or more lines of treatment, including rituximab, the following null hypothesis will be tested in the FAS:

```
H_{0, PFS}: S_{Copanlisib+Rituximab}(t) = S_{Placebo+Rituximab}(t) for all time points t \ge 0
```

The alternative hypothesis will be:

```
H1,PFS: S_{Copanlisib+Rituximab} (t) > S_{Placebo+Rituximab} (t) for at least one time point t \ge 0, and S_{Copanlisib+Rituximab} (t) \ge S_{Placebo+Rituximab} (t) for all time points t \ge 0,
```

where  $S_{Copanlisib+Rituximab}$  denotes the survival function of the copanlisib + rituximab group and  $S_{Placebo+Rituximab}$  denotes the survival function of the placebo + rituximab group in the total study population.

The following decision rule to test the null hypothesis will be applied:

According to the size of this study it is justified to assume under  $H_{0, PFS}$  the one-sided log-rank test (36) is a sufficiently close approximation to the normal distribution. If the z-value from the one-sided log-rank test (for the difference  $S_{Copanlisib+Rituximab}$  -  $S_{Placebo+Rituximab}$ , stratified by the factors used for randomization: FL vs. other iNHL histologies, and progression-free and treatment-free interval of  $\geq 12$  months after completion of the last rituximab-containing treatment vs. unwilling/unfit to receive chemotherapy) is larger than the critical quantile from the normal distribution ( $z_{0.975} = 1.96$ ), the null hypothesis will be rejected in favor of the alternative hypothesis.

The PFS will be tested in the hierarchy test (see Section 8.4.2.3).

### Additional analyses of the primary efficacy variable

Kaplan-Meier estimates of median times to PFS (including 95% confidence interval) and Kaplan-Meier curves will be presented for each treatment group.

The hazard ratios (including 95% confidence interval) will be derived from Cox proportional hazards models that are stratified by the same factors as used for the primary efficacy analysis.

The censoring mechanism of subjects without PFS event at the time of analysis is assumed to be non-informative for the primary efficacy analysis. Sensitivity analyses will be performed, assessing the impact of a potential informative censoring of such subjects. These will include

09 FEB 2023 Page: 94 of 151

the use of different rules for considering subjects without PFS events as having an event or being censored and will be further outlined in the SAP.

## 8.4.2.2 Secondary efficacy parameters

All secondary efficacy variables will be analyzed in the FAS at the time of the analysis of the primary variable.

The ORR will be analyzed using the Cochran-Mantel-Haenszel test (37), stratified for the same stratification factors as used for PFS. The null hypothesis is defined as:

 $H_{0, ORR}$ :  $ORR_{Copanlisib+Rituximab} \leq ORR_{Placebo+Rituximab}$ 

The alternative hypothesis is:

 $H_{1, ORR}$ :  $ORR_{Copanlisib+Rituximab} > ORR_{Placebo+Rituximab}$ 

The following decision rule to test the null hypothesis will be applied:

If the p-value for the two-sided Cochran-Mantel-Haenszel test is smaller than the 0.05 significance level and the estimated difference  $ORR_{Copanlisib+Rituximab}$  -  $ORR_{Placebo+Rituximab}$  (comparing copanlisib + rituximab vs. placebo + rituximab) is greater than 0.0, the null hypothesis will be rejected in favor of the alternative hypothesis.

The time to deterioration and time to improvement in DRS-P subscale of FLymSI-18 will be analyzed analogously to the PFS, using similar hypotheses, decision rules, and significance level.

OS, CRR, TTP as well as DOR will be analyzed supportively only.

OS, TTP, and DOR will be analyzed using stratified log-rank tests analogue to the analysis for the primary endpoint, PFS.

CRR will be analyzed using the Cochran-Mantel-Haenszel test and estimated difference analogous to the analysis of ORR. The test will be adjusted for the same stratification factors as used for PFS.

The first analysis of OS will be performed at the time of analysis of the primary endpoint, PFS. The survival status will further be collected quarterly during the survival follow-up period up to 7 years after the last patient started study treatment.

A follow-up analysis of OS will be performed. Details will be described in the SAP.

# 8.4.2.3 Confirmatory statistical test strategy

Separate statistical test strategies will be conducted for the United States and Europe as outlined below

#### **United States**

For the United States, to control the study-wise alpha, a fixed-sequence multiple testing strategy will be implemented. The sequence of the testing of primary and secondary endpoints will be as follows and is shown in Figure 8–1.

[figure not shown]
The primary efficacy variable PFS will be tested in the FAS population (tested at one-sided alpha=0.025).

If the PFS test in the FAS population is successful,

09 FEB 2023 Page: 95 of 151

- a) a second test on the PFS will be performed (tested at one-sided alpha=0.025), evaluating the subpopulation of combined FL and MZL population, if this is successful
- b) a test on the ORR in the combined FL and MZL population will be performed (tested at one-sided alpha=0.025), if this is successful
- c) a test on the time to deterioration in DRS-P in the combined FL and MZL population will be performed (tested at one-sided alpha=0.025), if this is successful
- d) a test on the time to improvement in DRS-P in the combined FL and MZL population will be performed (tested at one-sided alpha=0.025), it would conclude the confirmatory test procedure.

Figure 8–1 Confirmatory test strategy based on five test families for United States

09 FEB 2023 Page: 96 of 151

For testing Families 1 to 2 of this confirmatory test strategy, an assessment of power based on Schoenfeld's formula (52) was performed for two scenarios as listed in Table 8–1:

- Scenario 1: HR=0.61 in the FAS population (according to the re-planned sample size planning)
- Scenario 2: HR=0.53 in the FAS population (less conservative assumption)

Table 8–1 Assessment of statistical power for PFS test in the overall FAS population and combined FL and MZL population

	Total patients	Dropout rate	Events to be expected (E)	Hazard ratio	Power
Scenario 1:					
Family 1: overall FAS population	458	30%	190	0.61	89.5%
Family 2: combined FL and MZL population	370	30%	140	0.61	78.7%
Scenario 2:					
Family 1: overall FAS population	458	30%	190	0.53	98.5%
Family 2: combined FL and MZL population	370	30%	140	0.53	94.3%

The number of total patients in Table 8–1 is the number of patients having been randomized in the study.

### **Europe**

For Europe, to control the study-wise alpha, a fixed-sequence multiple testing strategy will be implemented. In this strategy, the sequence of the testing of primary and secondary endpoints is as follows and is shown in Figure 8–2:

The primary endpoint PFS will be tested in the FAS population (tested at one-sided alpha=0.025).

If the PFS test in the FAS population is successful,

- a) a second test on the ORR in the FAS population will be performed (tested at one-sided alpha=0.025), if this is successful,
- b) a test on the DRS-P deterioration in the FAS population will be performed (tested at one-sided alpha=0.025), if this is successful,
- c) a test on the DRS-P improvement in the FAS population will be performed (tested at one-sided alpha=0.025), it would conclude the confirmatory test procedure.

09 FEB 2023 Page: 97 of 151

Family 1 (F1)

PFS in iNHL population (FAS)
Alpha: 2.5%

ORR in iNHL population (FAS)
Tested, if success in F1
Alpha: 2.5%

DRS-P deterioration in iNHL population (FAS)
Tested, if success in F2EU
Alpha: 2.5%

Pamily 3 EU (F3EU)

DRS-P improvement in iNHL population (FAS)
Tested, if success in F3EU
Alpha: 2.5%

Figure 8-2 Confirmatory test strategy based on four test families for Europe

Note: EU refers to Europe

